8.3 Exploratory Outcomes

Objective	Outcome Measure
To compare the genomic landscape	This will be measured by quantifying the genomic
between paired samples (where these	aberrations in both the CSF cfDNA samples. The level
are available)	of agreement will be measures as the number of
	aberrations observed in both samples as a proportion
	of all aberrations observed.

IRAS ID: 286155 Page **31** of **73**

9. Participant Timelines and Assessments

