3.1. Schematic the Study

Prior to enrolment

Patient Identification: Patients with CNS involvement secondary to breast cancer identified via breast and neuro-oncology/neuro-surgical departments, multi-disciplinary teams and clinics at involved UK centres.

- Obtain patient consent

Inclusion Criteria

- Informed Consent
- Male or female
- ≥16 years of age
- Any ER, PgR or HER2 status
- Newly diagnosed with BCBM*
- Progressive BCBM following either local or systemic treatment*
 - o or
- · Leptomeningeal disease

Exclusion Criteria

- Where the investigator considers it unsafe to undertake a lumbar puncture or perform an aspiration from the Ommaya reservoir
- Unable to comply with study procedures or give informed consent
- Where the investigator considers it not in the best interest of the patient to participate

At registration

- Patient enrolled on study

When scheduled

- Data collection and Routine/Diagnostic Tissue Collection

As soon as possible after procedure

 a) CSF extraction Procedure (along with blood sample collection pre-lumbar puncture/Ommaya Reservoir aspiration)

At routine visit or over the phone

- Post-procedure complications assessment for clinician (as soon as is feasible on a paper or eCRF)
- b) Post-procedure complications assessment **for patient** (28 days ± 7 days post-procedure at routine clinical visit or via phone

Paired Sample Collection (n = 20 if possible): Patients will be consented for a paired sample collection where they will be required to attend a second visit for lumbar puncture or Ommaya Reservoir CSF collection after 3 months of first CSF extraction or at disease progression (cranial or non-cranial). Follow procedures a), b) and c).

All samples sent to the GCP Lab for storage until sample collection end.

Samples sent to Cancer Research Lab in Leicester for analysis

Follow up end, Study Outcome Measures

IRAS ID: 286155 Page **15** of **73**

4. Roles and Responsibilities

Sponsor

The Sponsor is the University of Liverpool and is legally responsible for the study. They will formally delegate specific sponsoring roles to the Chief Investigator and Clinical Trials Centre.

Funders

North West Cancer Research is the lead funder for this study. It is funding the feasibility study the collection of 40 CSF samples of CSF, storage at GCP Laboratories and analysis at the University of Leicester.

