9.2 Informed Consent

Informed consent is a process initiated prior to an individual agreeing to participate in the study and continues throughout the individual's participation. Informed consent is required for all patients participating in this study. In obtaining and documenting informed consent the investigator should adhere to GCP and to the ethical principles that have their origin in the Declaration of Helsinki. Discussion and explanation of the study, using the Patient Information Sheet should be provided to patients by staff with appropriate experience. An appropriate Patient Information Sheet and Consent Form, describing in detail the study procedures and risks will be approved by an ethics committee and the patient will be asked to read and review the document. Upon reviewing the document, the investigator will explain the research study to the patient and answer any queries that arise. A contact point where further information about the study may be obtained will be provided to the patient. If a potential participant does want to withdraw from the study, they do not have to give a reason.

Permission will be sought, and all patients will be required to give informed consent prior to any study procedures. Patients will be approached during their first or second clinic visit/appointment. Patients will be given time to consider the study, and if they wish to take part will be asked to sign the relevant consent form.

Consent will be obtained to take part in the study and to collect the following samples:

- Collection of available and future routinely collected Formalin Fixed Paraffin Embedded (FFPE) samples of primary breast cancer (from diagnostic biopsies), non-CNS metastasis (from diagnostic biopsies of brain metastases – where available) and brain metastasis (where available)
- Collection of Blood and Cerebrospinal Fluid sample¹
- Collection of a repeat Blood and Cerebrospinal Fluid sample can occur at the time of disease progression or if patient is well and responding to treatment at 3 months after the initial procedure.

IRAS ID: 286155 Page **32** of **73**

¹Patients having surgical resection of brain metastasis can have their lumbar puncture under general anaesthesia at start of procedure (where safe to do so). In addition, CSF can be collected at time of insertion of collection of Ommaya reservoir.

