9.5.1 Schedule of Study Procedures

	Screening & Registration (1st or 2nd visit)	First CSF Sample collection Visit*	2 nd CSF Sample Collection Visit*	Disease Progression OR Event driven Follow-up (e.g. Neurosurgery or relapse)**
Procedures				
Communication of study information & PIS	х			
Informed Consent	Х			
Check of Eligibility Criteria	х			
Confirmation of ER, PgR, HER2 status (primary breast cancer)***	х			
Data Collection				
Demographic Information	х			
Clinico-pathological information	х			
Prior Cancer Therapy (top line)	х			
Collection of data: At study entry and then subsequently when there is disease progression, treatment changes and	X			x

IRAS ID: 286155 Page **37** of **73**

death				
Diagnostic Biopsies				
Requesting and				
posting of FFPE				
Tissue:				
i) Collection of				
Primary Breast Biopsy				
and/or	X			v
ii) Collection of non-	*			X
CNS				
recurrent/metastatic				
tissue and/or				
ii) Collection of CNS				
Biopsy				
Blood and CSF				
Collection of blood				
samples:				
1 x 10ml EDTA blood				
tube		X	X	
1 x 10ml SERUM tube		^	^	
(prior to lumbar				
puncture with				
atraumatic needle)				
Lumbar Puncture				
Collection of:				
1 x 10ml CSF tube		X	x	
1 x 3ml - 5ml CSF			Α	
tube				
Questionnaire				
(Completed on				
patient's discharge)				

IRAS ID: 286155 Page **38** of **73**

Clinical complications			
questionnaire (clinical			
staff to complete on	Х	X	
eCRF)			
Questionnaire (28			
days ± 7 days post-			
lumbar puncture)			
Patient complications			
questionnaire (patient	Х	x	
to complete via phone	^	^	
or at routine visit)			

^{*}For initial and sequential CSF sample (at disease progression or if patient is well 3 months after first CSF extraction). This will be mentioned on the Patient Information Sheet and Consent Form.

IRAS ID: 286155 Page **39** of **73**

^{**}Data will be collected for all patients if there are changes in their progression, treatment or in the event of death up until study closure or patient withdrawal.

^{***}ER, PgR and HER2 status of all CNS and non-CNS metastatic (where available) collected will documented.

10. Procedures for all patients

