10.6 Second Lumbar Puncture / Ommaya Reservoir Aspiration Visit

Where a patient is undergoing a second CSF collection, this should be carried out either at disease progression or if the patient remains well – after 3 months of the first CSF extraction.

The following procedures should occur at this visit:

- Blood sample collection (1 x 10ml EDTA blood tube and 1 x 10ml SERUM tube) this should be collected immediately before the CSF extraction procedure
- CSF extraction (1 x 10ml CSF tube and 1 x 3ml 5ml CSF tube) this should be carried
 out via Lumbar Puncture or Ommaya Reservoir aspiration as per standard procedure
 (atraumatic needles should be used unless discussed with PI & CI)
- Clinical complications questionnaire (completed by clinical staff via eCRF)

Following this visit, the Follow-up visit should take place as per Section 10.4

IRAS ID: 286155 Page **41** of **73**

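### The paired-CSF overlap in section 8.3 cannot tell lost aberrations from gained ones, and no split by reason for the second sample is stated

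*Protocol*

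**What the plan says.** **Measure.** The exploratory objective in Protocol section 8.3 begins "To compare the genomic landscape" and concerns paired CSF samples where these exist. Aberrations are to be quantified in both samples. The level of agreement is the number of "aberrations observed in both samples as a proportion" of all those seen. No other outcome is dedicated to the paired samples.

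**When the second sample is taken.** Four places describe this:
- Section 9.2: the repeat sample "can occur at the time of disease progression or if patient is well and responding to treatment at 3 months after the initial procedure".
- Section 9.5.1, footnote: "at disease progression or if patient is well 3 months after first CSF extraction".
- Section 10.6: "this should be carried out either at disease progression or if the patient remains well", in the latter case after 3 months.
- Section 3.1: "after 3 months of first CSF extraction or at disease progression (cranial or non-cranial"; here the 3-month sample carries no condition that the patient be well.

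**Numbers and analysis.** Section 3.1 hopes for 20 pairs. Section 4 shows that the same funding may go to up to 40 single samples instead. Section 13.5 makes all analyses exploratory and descriptive, with continuous data given as median, IQR and range. No section separates pairs by the reason for the second sample, and none says that they will be merged into one figure.

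**The concern.** The two occasions for resampling are opposite clinical states. The protocol's own background (section 5.1) says that cfDNA has been used in extracranial disease to follow treatment response, and that CSF cfDNA can reveal resistance mechanisms at progression. Aberrations that vanish in a patient doing well and aberrations that appear at progression would be different findings. The stated index records both simply as less agreement.

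A reader given a low overlap could not say whether tumour DNA had fallen below detection or a different set of aberrations had emerged. Section 5.3.1 says that for most patients the CSF procedure is an extra one, so the outcome dedicated to the repeat sample should be able to make that distinction.

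**Working it through.** **1. The plan's own precision figure.** Section 13.2 gives a conservative standard error of 6% for a binary endpoint at 70 patients: √(0.5 × 0.5 / 70) = 0.0598. It reproduces. It applies to the whole study; no precision is stated for the paired outcome.

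**2. Symmetry of the index.** For one pair, let S be the aberrations in both samples, L those only in the first and G those only in the second. The section 8.3 measure is

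O = S / (S + L + G).

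L and G enter identically, so O cannot separate them. Illustrative counts (assumed; the documents give none):

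| Pair | S | L | G | O |
|---|---|---|---|---|
| Second sample has no detectable tumour DNA | 0 | 5 | 0 | 0/5 = 0% |
| Complete replacement | 0 | 5 | 5 | 0/10 = 0% |
| Three of five lost | 2 | 3 | 0 | 2/5 = 40% |
| Three gained on two | 2 | 0 | 3 | 2/5 = 40% |

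This holds whether O is read per pair or with counts summed over patients.

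**3. Dependence of an overall figure on the mix.** Let w be the share of pairs taken at progression. A patient-level mean is

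O_all = w × O_prog + (1 − w) × O_well.

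The overlap values are assumptions, chosen to show the range:

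| O_prog | O_well | w = 25% | w = 50% | w = 75% |
|---|---|---|---|---|
| 0.40 | 0.80 | 0.70 | 0.60 | 0.50 |
| 0.50 | 0.70 | 0.65 | 0.60 | 0.55 |
| 0.60 | 0.60 | 0.60 | 0.60 | 0.60 |
| 0.70 | 0.50 | 0.55 | 0.60 | 0.65 |

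The figure moves with the mix only if the groups differ, and the direction reverses with the assumption. If counts were summed over patients, pairs with more aberrations would weigh more. With an assumed 10 aberrations per progression pair and 4 per well pair, the first row becomes 0.62, 0.51 and 0.45.

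**4. Precision after a split.** Take p = 0.5, so that the SE is √(0.25/n). This is conservative, because a quantity between 0 and 1 has variance of at most 0.25.
- 20 pairs together: SE 11.2 points, 95% interval about ±1.96 × 11.2 = ±22 points.
- 10 pairs in a group: SE 15.8 points, about ±31 points.
- Difference between two groups of 10: ±1.96 × √(0.25/10 + 0.25/10), about ±44 points.

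**The case against.** Much of the case on the other side stands.

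- **Pooling is not stated.** Both samples most naturally means one patient's pair, and section 13.5 would then summarise the per-pair values by median and IQR. A reader might infer that the plan merges all pairs into one count-weighted figure; the text does not say so.
- **The mix does not replace genomic change.** A reader might go further and infer that the result would reflect who was resampled rather than genomic change. That is not supported. Each overlap compares two samples from the same patient and so carries within-patient change. The mix only sets the weights of an average, and has no effect if overlap is equal in the two groups.
- **Details may sit elsewhere.** Strata and the handling of samples without detectable tumour DNA are commonly left to a statistical analysis plan, which is not shown. Section 10.5 requires progression and treatment-change forms, so pairs could largely be classified from planned data. The CRFs are not shown either, so it cannot be said that the reason is unrecorded.
- **Lost and gained counts are derivable.** Section 8.3 quantifies aberrations in each sample before defining agreement.
- **The stakes are low.** This is an exploratory, descriptive outcome in about 20 pairs at best, and it plays no part in the feasibility criteria of section 13.4.

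What these points do not remove is the symmetry of the measure the protocol names. It is there under the per-pair reading too. Section 10.5 also asks for no follow-up data when nothing has changed, so on those forms alone a patient who is well is identified only by the absence of a form.

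**Conclusion.** The point holds, at minor severity. The agreement measure in section 8.3 cannot distinguish aberrations lost from aberrations gained, and it gives 0% both to a pair with no detectable tumour DNA in one sample and to complete replacement. This follows from the formula and needs no assumption.

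The second part is conditional. Because resampling occurs in two clinical states and no split is stated, an overall summary would also depend on the unplanned mix if overlap differs between them. The size and direction are unknown: the illustrations run from a fall of 20 points, through no change, to a rise of 10 points as the progression share goes from 25% to 75%, all on assumed overlaps.

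**What to change.** In section 8.3:
1. State that overlap is computed per patient.
2. Report the numbers of shared, lost and gained aberrations for each pair.
3. Describe these separately for second samples taken at progression and at 3 months while well, with the number of pairs in each group. Show cranial and non-cranial progression by listing only.
4. List pairs with no detectable tumour DNA in one sample on their own, outside the overlap summary.
5. Make sure the reason for each second sample is recorded when it is taken. Sections 3.1, 9.2, 9.5.1 and 10.6 describe the 3-month occasion differently and should be reconciled so that the categories are clear.

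The cost is a few lines of outcome wording and, if it is not already collected, one data item. The downside is small groups: about ±31 points at 10 pairs each, wider if fewer pairs are obtained. The split should therefore be presented as description, without a formal comparison of the groups.

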9.1 Participant Identification

Patients will be identified by the oncologist, neurologist, neuro-oncologist or clinical staff in direct care of the patient. Once a site has been greenlighted, the necessary research team members will be made aware of the inclusion criteria of the study.

9.2 Informed Consent

Informed consent is a process initiated prior to an individual agreeing to participate in the study and continues throughout the individual's participation. Informed consent is required for all patients participating in this study. In obtaining and documenting informed consent the investigator should adhere to GCP and to the ethical principles that have their origin in the Declaration of Helsinki. Discussion and explanation of the study, using the Patient Information Sheet should be provided to patients by staff with appropriate experience. An appropriate Patient Information Sheet and Consent Form, describing in detail the study procedures and risks will be approved by an ethics committee and the patient will be asked to read and review the document. Upon reviewing the document, the investigator will explain the research study to the patient and answer any queries that arise. A contact point where further information about the study may be obtained will be provided to the patient. If a potential participant does want to withdraw from the study, they do not have to give a reason.

Permission will be sought, and all patients will be required to give informed consent prior to any study procedures. Patients will be approached during their first or second clinic visit/appointment. Patients will be given time to consider the study, and if they wish to take part will be asked to sign the relevant consent form.

Consent will be obtained to take part in the study and to collect the following samples:

- Collection of available and future routinely collected Formalin Fixed Paraffin Embedded (FFPE) samples of primary breast cancer (from diagnostic biopsies), non-CNS metastasis (from diagnostic biopsies of brain metastases – where available) and brain metastasis (where available)
- Collection of Blood and Cerebrospinal Fluid sample¹
- Collection of a repeat Blood and Cerebrospinal Fluid sample can occur at the time of disease progression or if patient is well and responding to treatment at 3 months after the initial procedure.

IRAS ID: 286155 Page **32** of **73**

¹Patients having surgical resection of brain metastasis can have their lumbar puncture under general anaesthesia at start of procedure (where safe to do so). In addition, CSF can be collected at time of insertion of collection of Ommaya reservoir.

Informed consent should be re-affirmed throughout the study and all discussions and consent should be documented appropriately. The original signed document will be retained in the trial site's Investigator Site File (ISF) and copies will be made:

- One copy provided to the patient for their information,
- One copy transferred to the CTC via portal upload or encrypted email
- One copy filed in the participant's medical records paper/electronic.

N.B. Details of the consent process (date, persons involved, version and type of information sheet and consent form used) must also be recorded directly into the participant's medical records.

IRAS ID: 286155 Page **33** of **73**

9.3 Eligibility Assessment and Confirmation

Eligibility should be confirmed by an appropriately qualified member of the research team who is named on the delegation log. This must not occur until informed consent is documented. Eligibility Criteria are described in detail in Section 7.

Eligibility confirmation must be documented in the participant's medical notes and then on the relevant study CRF.

9.4 Patient Recruitment, Screening and Enrolment

Potential study participants will be identified from patients who meet the inclusion criteria.

Patients will be provided with a patient information sheet and the accompanied informed consent form during clinic visits or by post/email following appropriate discussion with a member of the research team. The clinical research team will be available in person or by phone to discuss information relating to the study to interested patients.

After sufficient time for review and consideration of the trial, patients will return to the clinic to address any questions and will be asked to provide informed written consent. Please note that in exceptional circumstances (i.e. when a patient lives far away from site or when the patient shows full understanding of the study and is agreeable to take part in the study) consent may be taken within the first visit.

Investigators should complete eligibility screening based on inclusion/exclusion criteria outlined in section 7 of this protocol. During the screening visit the following reviews/investigations will take place to ensure eligibility of patients to participate into the study (see Section 7 for full eligibility criteria)

After a patient has been screened, their details MUST be entered onto the eCRF database by the clinical study staff to register the patient and generate a Study ID for patient.

Participants will be registered via a secure (24-hour) web-based eCRF system controlled centrally by the LCTC. A personal login username and password provided by the LCTC will be required to access the registration system. Designated research staff will be issued with their personal login and password upon completion of training in the use of the system. This training will be coordinated by the LCTC. A Work Instruction will also be provided to sites to support the registration process.

IRAS ID: 286155 Page **34** of **73**

When the system requirements (i.e. consent, eligibility) are confirmed the participant registration and a unique study number will be displayed on a secure webpage. An automated email confirmation will be sent to the authorised Principal Investigator and PRIMROSE team.

PRIMROSE Registration Details:

Web access: https://www.lcturedcap.org.uk/redcap/

[contact]

Email: [contact]

(Note that LCTC is open between 0900-1700, Monday – Friday, excluding public holidays)

In the event of a registration system failure, the centre should contact the coordinating team at the LCTC (Monday to Friday between 9:00 to 17:00 excluding bank holidays) to try to resolve the problem. If the problem cannot be resolved the coordinating LCTC will perform central registration and provide the details over the phone.

To enable monitoring of the consent process and registration of patient, the following study documents should be forwarded to the LCTC by the Investigator/research site team within 2 days of a patient registration:

A copy of the Signed Consent Form signed by both the patient and the investigator

The documents should be uploaded to the PORTAL/emailed to the LCTC on Monday - Friday from 09:00 to 17:00 GMT, email: [contact]. Prior to sending documents, site staff should [contact] to inform the LCTC staff of the incoming registration.

The patient's GP and referring consultant will be informed of patient's decision to participate in the study.

9.5 Assessments and Follow-up

Once the patient has been registered on the PRIMROSE CSF study, the patient will be scheduled in for a lumbar puncture (with atraumatic needles) or aspiration of CSF from Ommaya Reservoir procedure as soon as is reasonably possible or at the time of neurosurgery if this planned or has been scheduled as part of routine care.

IRAS ID: 286155 Page **35** of **73**

The schedule of assessments is outlined below. The following research data and samples will be collected from the patient:

IRAS ID: 286155 Page **36** of **73**

9.5.1 Schedule of Study Procedures

	Screening & Registration (1st or 2nd visit)	First CSF Sample collection Visit*	2 nd CSF Sample Collection Visit*	Disease Progression OR Event driven Follow-up (e.g. Neurosurgery or relapse)**
Procedures				
Communication of study information & PIS	х			
Informed Consent	Х			
Check of Eligibility Criteria	х			
Confirmation of ER, PgR, HER2 status (primary breast cancer)***	х			
Data Collection				
Demographic Information	х			
Clinico-pathological information	х			
Prior Cancer Therapy (top line)	х			
Collection of data: At study entry and then subsequently when there is disease progression, treatment changes and	X			x

IRAS ID: 286155 Page **37** of **73**

death				
Diagnostic Biopsies				
Requesting and				
posting of FFPE				
Tissue:				
i) Collection of				
Primary Breast Biopsy				
and/or	X			v
ii) Collection of non-	*			X
CNS				
recurrent/metastatic				
tissue and/or				
ii) Collection of CNS				
Biopsy				
Blood and CSF				
Collection of blood				
samples:				
1 x 10ml EDTA blood				
tube		X	X	
1 x 10ml SERUM tube		^	^	
(prior to lumbar				
puncture with				
atraumatic needle)				
Lumbar Puncture				
Collection of:				
1 x 10ml CSF tube		X	x	
1 x 3ml - 5ml CSF			Α	
tube				
Questionnaire				
(Completed on				
patient's discharge)				

IRAS ID: 286155 Page **38** of **73**

Clinical complications			
questionnaire (clinical			
staff to complete on	Х	X	
eCRF)			
Questionnaire (28			
days ± 7 days post-			
lumbar puncture)			
Patient complications			
questionnaire (patient	Х	x	
to complete via phone	^	^	
or at routine visit)			

^{*}For initial and sequential CSF sample (at disease progression or if patient is well 3 months after first CSF extraction). This will be mentioned on the Patient Information Sheet and Consent Form.

IRAS ID: 286155 Page **39** of **73**

^{**}Data will be collected for all patients if there are changes in their progression, treatment or in the event of death up until study closure or patient withdrawal.

^{***}ER, PgR and HER2 status of all CNS and non-CNS metastatic (where available) collected will documented.

10. Procedures for all patients

